5.3. Other Evaluations

[REDACTED]

5.3.2. Dermal Imaging

Medical photography as supportive evidence of clinical outcome will be conducted by all sites using Canfield equipment. Photos will be obtained according to the Schedule of Visits and Assessments ([Section 1.3](#)). Photography should be focused on single lesions or specific body sections (e.g., scalp). Body or half body photos should only be taken if necessary. Every effort should be made to prioritize obtaining a photograph of the scalp lesion(s). All efforts will be made to de-identify the subjects. Subjects who are unwilling to participate in the medical photography will be allowed to opt out of this procedure and documented on the informed consent. Refer to the current Photography Manual for instructions regarding photography.

5.4. Final Study Visit

The approximate final study visit will occur at Week 8 (Day 57). The procedures performed during this visit are described in the Schedule of Visits and Assessments ([Section 1.3](#)). A 5-day scheduling window is allowed for this visit. Adverse events will be recorded as reported by the subject and followed to resolution (as necessary) as outlined in [Section 5.7](#).

5.5. Early Termination Visit

If a subject is withdrawn from the study, an early termination visit will be scheduled. This visit should include the procedures and assessments that would be performed at the Week 8 visit (Day 57). Subjects who withdraw consent from study participation, will not be required to perform an early termination visit.

5.6. Unscheduled Visit

Unscheduled visits may be necessary to repeat testing following abnormal laboratory results, for follow-up of AEs, or for any other reason, as warranted in the judgement of the Investigator.

The following information will be collected for all subjects:

- Concomitant medications/procedures
- AEs

5.7. Adverse Events

5.7.1. Adverse Event Definition

An AE is defined as any untoward medical occurrence associated with the use of a drug in humans, whether or not considered drug related. An AE can therefore be any unfavorable and unintended sign (including an abnormal laboratory finding), symptom, or disease temporally associated with the use of an investigational product, whether or not related to the investigational product.

The definition of AEs includes worsening of a pre-existing medical condition. Worsening indicates that the pre-existing medical condition has increased in severity, frequency, and/or duration or has an association with a worse outcome. When recording such events, provide descriptions that the pre-existing condition has changed (e.g., worsening hypertension for a subject with pre-existing hypertension). A pre-existing condition that has not worsened during the study or involves an intervention, such as elective cosmetic surgery or a medical procedure while on study, is not considered an AE.

Progression of treatment indication including new or worsening of anticipated clinical signs or symptoms, which are collected as clinical efficacy variables and assessed as unequivocally associated with the disease progression and /or lack of efficacy, should NOT be reported as adverse events unless the disease progression is greater than anticipated in the natural course of the disease.

In general, abnormal laboratory findings without clinical significance (based on the Investigator's judgment) are not to be recorded as AEs. However, abnormal laboratory findings that result in new or worsening clinical sequelae, or that require therapy or adjustment in current therapy, are considered AEs. Where applicable, clinical sequelae (not the laboratory abnormality) are to be recorded as the AE.

5.7.2. Serious Adverse Event

The definitions and reporting requirements of the Food and Drug Administration (FDA)/ICH Guidelines for Clinical Safety Data Management, Definitions and Standards for Expedited Reporting, Topic E2A will be adhered to. Mandatory reporting of all serious unexpected adverse drug reactions (SUSARs) to Health Canada [as per C.05.014 (1) of the FDR] will be adhered. If any AEs are serious, as defined by ICH Guidelines for Clinical Safety, required procedures will be followed.

An SAE is defined as any AE that, in the view of either the PI or Sponsor, meets at least 1 of the following serious criteria:

- Fatal
- Life-threatening (places the subject at immediate risk of death)
- Requires inpatient hospitalization or prolongation of existing hospitalization
- Results in a persistent or significant incapacity/disability
- Congenital anomaly/birth defect
- Other important medical events that, based upon appropriate medical judgment, may jeopardize the subject and may require medical or surgical intervention to prevent one of the outcomes listed in the above definition

Hospitalization does not include the following:

- Rehabilitation facilities, hospice facilities or respite care (e.g., caregiver relief)
- Nursing homes or skilled nursing facilities
- Emergency department visits
- Same day surgeries (as outpatient/same day/ambulatory procedures)
- <24 hour admissions for observation or evaluation

Hospitalization or prolongation of hospitalization in the absence of a precipitating, clinical AE is not in itself an SAE. Examples include:

- Admission for treatment of a preexisting condition that did not worsen
- Hospitalizations for cosmetic elective surgery, social, and/or convenience admissions
- Pre-planned treatments or surgical procedures should be noted in the Baseline documentation for the individual subject
- Diagnostic and therapeutic procedures, such as surgery, should not be reported as AEs; however, the medical condition for which the procedure was performed should be reported if it occurs during the reporting period and meets the definition of an AE. For example, an acute appendicitis that begins during the AE reporting period should be reported as an AE, and the resulting appendectomy should be recorded as treatment of the AE.

Unexpected is defined as an AE that is not listed in the Investigator Brochure (IB) or is not listed at the specificity or severity that has been observed; or is not consistent with the risk information described in the general investigational plan or study documentation.

5.7.3. Suspected Unexpected Serious Adverse Reaction (SUSAR)

SUSAR is defined as a serious adverse reaction, the nature or severity of which is not consistent with the known study treatment information. A serious event or reaction is not defined as a SUSAR when: ‘it is serious but expected’ or it does not fit the definition of an SAE, whether expected or not.

5.7.4. Safety Review with Subject

At each subsequent clinic visit after the Screening visit, subjects will be queried with an open-ended question such as: ‘How have you been feeling since your last visit?’ Additionally, the study staff will review subject diaries and, if it appears that a potential AE was recorded, study staff will query the subject and determine if an AE occurred.

5.7.5. Adverse Event Reporting

The Investigator is responsible for recording all adverse events, observed by the clinic staff, or reported by the subject that occur after the first application of investigational product through 30 days after end of treatment are recorded in the subject’s medical record and the eCRF.

Serious adverse events observed by the clinic staff or reported by the subject after signing the informed consent form will be recorded.

All adverse events that meet the criteria for “serious” (i.e., SAEs) will be reported to the Sponsor via fax or e-mail to [REDACTED].com within 24 hours of becoming aware of the event, whether or not the serious events are deemed IP-related.

All serious event reporting will adhere to ICH E6: Guideline for Good Clinical Practice and ICH E2A: Clinical Safety Data Management: Definitions and Standards for Expedited Reporting. The Institutional Review Board (IRB) will be notified of the Alert Reports as per FDA, ICH and the IRB’s policies and procedures.

The Sponsor, or delegate, will be responsible for reporting SAEs to health authorities per local reporting requirements. The Investigator will be responsible for reporting events to their respective IRBs/ Ethics Review Board (ERB) in accordance with the IRB/ERB requirements.

AEs (whether serious or non-serious) and clinically significant abnormal laboratory test value(s) will be evaluated by the PI and treated and/or followed for 30 days after end of treatment until the symptoms or value(s) return to the subject’s Baseline value, or acceptable levels, as judged by the Investigator. Where appropriate, medical test(s) and/or examination(s) will be performed to document resolution of event(s).

The Investigator will review each adverse event and assess its relationship to Investigational Product (unrelated, unlikely, possibly, probably, likely). Each sign or symptom reported will be graded on the NIH NCI CTCAE toxicity grading scale 5-point severity scale (Grade 1, 2, 3, 4 and 5). The date and time of onset, time relationship to drug dosing, duration, and outcome) of each event will be noted.

The relationship of each AE to the Investigational Product will be assessed using the following definitions:

Unrelated	The AE must clearly be caused by the subject's clinical state, or the study procedure/conditions. Definitely not related to drug. Temporal sequence of an AE onset relative to administration of drug not reasonable. Another obvious cause of an AE.
Unlikely	Time sequence is unreasonable. There is another more likely cause for an AE.
Possibly	Corresponds to what is known about the drug. Time sequence is reasonable. Could have been due to another equally, likely cause.
Probably	Is a known effect of the drug. Time sequence from taking drug is reasonable. Ceases on stopping the drug. Cannot be reasonably explained by the known characteristics of the subject's clinical state.
Likely	Is a known effect of the drug (e.g., listed in Physicians' Desk Reference, Compendium of Pharmaceuticals and Specialties, IB). Time sequence from taking drug is reasonable. Event stops upon stopping drug, event returns upon restarting drug.

The following CTCAE toxicity grading scale 5-point severity scale definitions for rating maximum severity will be used:

Grade 1	Mild; asymptomatic or mild symptoms; clinical or diagnostic observations only; intervention not indicated.
Grade 2	Moderate; minimal, local or noninvasive intervention indicated; limiting age-appropriate instrumental activities of daily living.*
Grade 3	Severe or medically significant but not immediately life-threatening; Hospitalization or prolongation of hospitalization indicated; disabling; limiting self-care activities of daily living.** Note: An experience may be severe but may not be serious, e.g., severe headache).
Grade 4	Life-threatening consequences; urgent intervention indicated.
Grade 5	Death related to AE.

Footnotes from table above:

Note: A semi-colon indicates 'or' within the description of the grade.

* Instrumental activities of daily living refer to preparing meals, shopping for groceries or clothes, using the telephone, managing money, etc.

** Self-care activities of daily living refer to bathing, dressing and undressing, feeding self, using the toilet, taking medications, and not bedridden.

AEs will be coded using the most current MedDRA® version available at the start of the study.

5.8. Reporting Pregnancy

During study participation, all subjects should be instructed to contact the Investigator immediately if they suspect they might be pregnant (e.g., missed or late menstrual period). If pregnancy is confirmed, Investigational Product must be discontinued immediately, the subject should be referred to an obstetrician experienced in reproductive toxicity for evaluation and counseling, and the subject should be followed until conclusion of the pregnancy.

The Investigator is responsible for reporting all available pregnancy information on the pregnancy report to [REDACTED] within 24 hours of becoming aware of the event, although pregnancy itself is not considered an AE. Follow-up information detailing the outcome of the pregnancy and the health of the newborn should be reported as it becomes available. In addition, any pregnancy resulting in a congenital abnormality or birth defect of the newborn, or neonatal death occurring within 30 days of the birth must be reported as a SAE, regardless of causality.

Partner pregnancies of a male subject do not need to be reported.

5.9. Treatment Stopping Rules

If a subject has non-cutaneous adverse events of concern, clinically significant laboratory values or any condition that the Investigator determines could possibly be related to the investigational product, the Investigator should immediately contact the Medical Monitor to discuss if the subject should be discontinued from treatment with investigational product.

Treatment for any individual subject will be discontinued if the subject experiences:

- A SAE or a clinically significant non-serious AE which in the opinion of the Principal Investigator or Medical Monitor warrants discontinuation from the study for that subject's well-being
- A treatment-emergent severe (Grade 3) laboratory abnormality (confirmed by repeat sample) which in the opinion of the Principal Investigator or Medical Monitor warrants discontinuation from the study for that subject's well-being

A subject with a PHQ-8/PHQ-A score ≥ 15 should receive immediate referral to a mental health care professional, and Investigators in consultation with the mental health professional should consider interruption or discontinuation of the investigational product.

- Subjects with a PHQ-8 or modified PHQ-A score of 10-14 should be referred to a mental health professional for evaluation, regardless of the reason for their change in score

A subject that is experiencing suicidal ideation and behavior should be referred immediately to a qualified mental health care provider and consideration given to discontinuation from IP.

As noted above, IP must be discontinued immediately in the event of a female subject's pregnancy.

IP Treatment should be interrupted:

- If a subject develops an application site reaction with the clinical appearance of an 'irritation reaction', and with a severity of a Dermal Response Score of 5 (erythema, edema, and papules) or greater on the scale of Berger and Bowman, treatment should be interrupted for up to one week and may then be resumed if the reaction has, in the opinion of the Investigator, adequately resolved.

IP Treatment should be discontinued:

- If the reaction reoccurs. IP should be discontinued permanently, and the subject followed until the reaction resolves.

For cases of suspected allergic contact dermatitis, the medical monitor and sponsor should be notified and there should be discussion about performing patch testing to further evaluate. Patch testing is encouraged in such cases.

In the event of a medical emergency where unblinding is required to provide medical care to the subject, refer to the most current IWRS Plan and Breaking Treatment Codes ([Section 4.8.5](#)). Contact the Medical Monitor and the Sponsor promptly.

6. DATA ANALYSIS

Data will be handled and processed according to the Contract Research Organization's (CRO) Standard Operating Procedures, which are written based on the principles of GCP.

6.1. Statistical Methods

The methodology presented below is a summary of the more detailed analysis plan that will be presented in the Statistical Analysis Plan (SAP). The SAP will be finalized before the database is locked and unblinded. Any changes to the methods described in the final SAP will be described and justified in the clinical study report.

All statistical processing will be performed using SAS[®] (Version 9.4 or later) unless otherwise stated.

Subjects will be stratified by study site, Baseline S-IGA (3 vs. 4), and Baseline B-IGA (2 vs. ≥ 3).

6.1.1. Determination of Sample Size

A sample size of up to approximately 420 subjects is planned for the study.

The randomization scheme will be 2:1 (ARQ-154 foam 0.3% QD: matching vehicle QD). Approximately 280 subjects will receive ARQ-154 foam 0.3% QD; approximately 140 subjects will receive vehicle foam QD.

This sample size provides more than 99% power to detect an overall 35% difference between treatment groups on S-IGA success at Week 8 and an overall 25% difference between treatment groups on B-IGA success at Week 8 at $\alpha=0.025$ using a 2-sided stratified (B-IGA at randomization, S-IGA at randomization and study site) Cochran-Mantel-Haenszel test. The results from a recent phase 2 study (ARQ-154-204) of ARQ-154 foam 0.3% compared to vehicle treatment were used to estimate the treatment difference.

The number of subjects to be enrolled will also provide at least 90% power for most of the secondary endpoint analyses. Additionally, the larger study size is included in order to provide additional/sufficient numbers of subjects on ARQ-154 treatment for a safety database.

6.1.2. Interim Analysis

No interim analyses are planned.

6.1.3. Background and Demographic Characteristics

Descriptive statistics will be presented for the subject disposition, demographics, Baseline characteristics, treatment compliance, efficacy endpoints and safety data collected in the clinical study. This includes the number and percentage of subjects for binary endpoints/categorical data, and mean, SD, median, Q1, Q3, minimum, and maximum for continuous data.

6.1.4. Study Disposition

Number of subjects randomized, receiving IP, completing study, and withdrawing prematurely (with reason for withdrawal) will be summarized by treatment group.

6.1.5. Protocol Deviations and Eligibility Deviations

The number of subjects with important protocol deviations and/or eligibility deviations will be summarized in categories by treatment group.

6.1.6. Investigational Product Application Compliance

The number of IP applications by each subject based on diary data will be summarized using descriptive statistics.

The amount of IP used by each subject based on can weight will be summarized by treatment using descriptive statistics.

IP dose compliance will be calculated based on number of applications divided by the expected number (amount) of IP applications for each subject. Compliance will be summarized descriptively by treatment group. Amount of IP (weight) used will also be summarized.

6.2. Safety Analysis

Descriptive statistics will be calculated for quantitative safety data and frequency counts will be compiled for classification of qualitative safety data. The safety population will be used for these analyses.

6.2.1. Adverse Events

Adverse events (AEs) will be summarized by preferred term, system organ class, and treatment group for all AEs, serious AEs, related AEs, AEs leading to withdrawal from investigational product, and AEs leading to withdrawal from study.

6.2.2. Clinical Laboratory Results

Shifts in clinical laboratory parameters from Baseline to worst post-Baseline grade will be provided.

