To start, Family 2 will be tested, sequentially within Family 2, each endpoint at the $\alpha=0.005$ level. Should the testing succeed through all seven endpoints in Family 2, the $\alpha=0.005$ will remain unused, and will be passed to Family 1.

The testing of the five SI-NRS endpoints in Family 1 will be sequential, either at the $\alpha=0.01$ level (assumes Family 2 had an unsuccessful test), or the $\alpha=0.015$ level (assumes all endpoints in Family 2 were successful at the $\alpha=0.005$ level).

Family 3 contains six endpoints. Family 3 has initially been allocated $\alpha=0.01$. This creates three possible testing alpha levels for the Family 3 endpoints:

- If all tests in Family 1 ($\alpha=0.01$) and Family 2 ($\alpha=0.005$) are successful, then $\alpha=0.005+0.01=0.015$ is unused, and the $\alpha=0.015$ will be carried to Family 3, allowing Family 3 endpoints to be tested at the full 0.025 level.
- If the $\alpha=0.005$ in Family 2 is used, but the subsequent $\alpha=0.01$ allocated to Family 1 is not used, then Family 3 endpoints will be tested at the $\alpha=0.01+0.01=0.02$ level.
- If the $\alpha=0.01$ in Family 1 is used, and the $\alpha=0.005$ in Family 2 is also used, then Family 3 endpoints will be tested at $\alpha=0.01$.

Descriptive statistics will be presented for endpoint and safety data collected in the clinical study. This includes the number and percentage of subjects for binary endpoints/categorical data, and mean, SD, median, Q1, Q3, minimum, and maximum for continuous data.

All subjects who are randomized and receive at least one confirmed dose of investigational product will be included in the safety population.

Adverse events (AEs) will be summarized by preferred term, system organ class, and treatment group for all treatment-emergent AEs, serious AEs, related AEs, AEs leading to withdrawal from investigational product.

Safety laboratory parameters and vital signs will be summarized at each visit using descriptive statistics or frequencies and percentages, as appropriate. Changes from Baseline and percent changes from Baseline in laboratory values and vital signs will also be summarized by visit. In addition, changes from Baseline and percent changes from Baseline in weight and laboratory values will be summarized using shift tables.

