6.1.5. Analysis Visit Windows

6.1.5.1. Non-Diary Assessments

Visits will be analyzed as scheduled (i.e., not subject to visit windowing). Unscheduled, early termination, and/or repeated measurements will only be included if a scheduled measurement is not available and the unscheduled, early termination, or repeated measurement falls within the analysis visit windows as described in [Table 2](#). Visits falling outside of these windows will not be windowed (e.g., an unscheduled visit before first application of study drug). The windows follow the Schedule of Events in [Table 1](#). Unscheduled/repeated measurements will be listed.

Table 2: Analysis Visit Windows (Study Visit) for Non-diary Assessments

| Visit Name | Visit Number | Target Start Day | Lower Limit | Upper Limit |
|------------|--------------|------------------|-------------|-------------|
| Week 2 | 3 | 15 | 2 | 22 |
| Week 4 | 4 | 29 | 23 | 42 |

| Visit Name | Visit Number | Target Start Day | Lower Limit | Upper Limit |
|------------|--------------|------------------|-------------|-------------|
| Week 8 | 5 | 57 | 43 | --- |

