9.3. Clinical Laboratory Evaluations

Laboratory test results will be summarized descriptively by treatment and study visit as both observed values, change and percent change from baseline values for continuous hematology, chemistry, and urinalysis results. Categorical urinalysis results will be summarized using frequencies by study visit and treatment.

The number of subjects with clinical laboratory values below, within, or above the normal range by study visit and in relation to baseline will be tabulated for each clinical laboratory analyte by treatment group (shift table).

Abnormal results will be flagged in the listings.

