| 14.2.11.1 | ITT | Summary, Change, and Percent Change from Baseline in Extent of Scalp Involvement by Study Visit - Observed Data |
| 14.3 | Safety Summary | |
| 14.3.1.1 | Safety | Overall Summary of Treatment Emergent Adverse Events |
| 14.3.1.2 | Safety | Treatment Emergent Adverse Events by System Organ Class and Preferred Term |
| 14.3.1.3 | Safety | Treatment Emergent Adverse Events by System Organ Class, Preferred Term, and Maximum Severity |
| 14.3.1.4 | Safety | Treatment Emergent Adverse Events by System Organ Class, Preferred Term, and Relationship to Study Drug |
| 14.3.1.5 | Safety | Treatment Emergent Adverse Events by Preferred Term |
| 14.3.1.6 | Safety | Treatment Emergent Serious Adverse Events by System Organ Class and Preferred Term |
| 14.3.1.7 | Safety | Treatment Emergent Adverse Events Leading to Study Drug Discontinuation by System Organ Class and Preferred Term |
| 14.3.1.8 | Safety | Treatment Emergent Adverse Events Leading to Study Discontinuation by System Organ Class and Preferred Term |

| | | |
|-------------|-----------------------------|--|
| 14.3.2.1 | Safety | Quantitative Summary of Investigator Local Tolerability Assessment (Dermal Response) by Study Visit |
| 14.3.2.2 | Safety | Categorical Summary of Investigator Local Tolerability Assessment (Dermal Response) by Study Visit |
| 14.3.2.3 | Safety | Categorical Summary of Investigator Local Tolerability Assessment (Other Effects) by Study Visit |
| 14.3.2.4 | Safety | Quantitative Summary of Subject Local Tolerability Assessment by Study Visit |
| 14.3.2.5 | Safety | Categorical Summary of Subject Local Tolerability Assessment by Study Visit Categorical Results |
| 14.3.3.1 | Safety | Summary of Clinical Chemistry Laboratory Results (Standard Units) by Study Visit |
| 14.3.3.2 | Safety | Shift from Baseline in Clinical Chemistry Laboratory Results (Standard Units) by Study Visit |
| 14.3.3.3 | Safety | Summary of Hematology Laboratory Results (Standard Units) by Study Visit |
| 14.3.3.4 | Safety | Shift from Baseline in Hematology Laboratory Results (Standard Units) by Study Visit |
| 14.3.3.5 | Safety | Summary of Quantitative Urinalysis Laboratory Results (Standard Units) by Study Visit |
| 14.3.3.6 | Safety | Shift from Baseline in Quantitative Urinalysis Laboratory Results (Standard Units) by Study Visit |
| 14.3.3.7 | Safety | Summary of Qualitative Urinalysis Laboratory Results by Study Visit |
| 14.3.4.1 | Safety | Summary of Vital Signs by Study Visit |

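### The SAP omits the protocol's laboratory shift to worst post-baseline grade, plans only low/normal/high shifts by visit, and does not record the change

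*Protocol*

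**What the plan says.** Protocol 6.2.2 is a single sentence: "Shifts in clinical laboratory parameters from Baseline to worst post-Baseline grade will be provided". Protocol 6.3.2, repeating the synopsis, adds in general terms that "changes from Baseline and percent changes from Baseline in weight and laboratory values will be summarized using shift tables".

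SAP 9.3 plans descriptive summaries by visit and one kind of shift table, in which "clinical laboratory values below, within, or above the normal range by study visit and in relation to baseline will be tabulated". The matching outputs in SAP 14.1 are Tables 14.3.3.2, 14.3.3.4 and 14.3.3.6, for chemistry, hematology and quantitative urinalysis. The first is titled "Shift from Baseline in Clinical Chemistry Laboratory Results (Standard Units) by Study Visit" and the other two follow the same form.

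For every assessment that is not a diary, SAP 6.1.5.1 states: "Unscheduled, early termination, and/or repeated measurements will only be included if a scheduled measurement is not available". The result must also fall in the analysis window. For the rest, "Unscheduled/repeated measurements will be listed".

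**The concern.** The protocol's table has two features: a grade, and the worst value over the whole post-baseline period. The SAP keeps neither. A low/normal/high category cannot separate a slight excursion from a severe one, and a by-visit table never forms a subject's worst value.

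The windowing rule adds to this. The protocol expects extra samples: Section 5.1.6 allows unscheduled laboratory tests, and Section 5.6 names repeat testing after an abnormal result as a reason for an unscheduled visit. Those samples are taken because something looked abnormal, and they are the ones most likely to stay outside the tables.

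Safety is part of the primary objective, and SAP 3.2 gives the safety database as a reason for the trial's size. What is at stake is whether the report can compare the arms on the severity of laboratory worsening.

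**Working it through.** The plan gives no figure to reproduce here. The check sets the passages side by side and applies the windowing rule case by case.

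**1. Grade.** Protocol 6.2.2 asks for grade; SAP 9.3 uses three range categories. No laboratory grade appears in SAP 9.3 or in Tables 14.3.3.1 to 14.3.3.7. Neither document names a grading scale for laboratory values; CTCAE is named only for adverse events (Protocol 5.7.5).

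**2. Worst value.** Suppose that in one arm a subjects are above range at Week 4 and b at Week 8. The number above range at either visit lies anywhere from max(a, b) to a + b (capped at the arm size). By-visit counts do not determine it, so even the incidence of any post-baseline excursion cannot be read from these tables.

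**3. Subjects out of range at baseline.** Exclusion criterion 10 (Protocol 4.5.2) excludes AST or ALT above 2x ULN. A value above 1x and up to 2x ULN passes that criterion and is coded above range at baseline. Any later value above ULN is also coded above range. A stable value and a large rise therefore fall in the same cell, above to above.

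**4. Unscheduled and repeat results.** Post-baseline laboratory draws are scheduled only at Weeks 4 and 8 (Protocol 1.3; SAP Table 1). The windows come from SAP Table 2.

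| Extra result | Scheduled value available in that window? | Enters the by-visit tables? |
|---|---|---|
| Days 2 to 22 (Week 2 window) | No draw is scheduled | May enter as Week 2 |
| Days 23 to 42, Week 4 draw done | Yes | No, listing only |
| Day 43 onward, Week 8 draw done | Yes | No, listing only |
| Day 23 onward, that window's draw missed | No | May enter |

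A repeat of an abnormal Week 4 or Week 8 draw within the same window is always left out, because the abnormal scheduled value is itself available. A repeat of a Week 4 draw that falls on Day 43 or later is also left out, unless the Week 8 draw was missed.

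**5. Record of change.** SAP 11.1 records added populations, added exploratory endpoints and a changed PK population. SAP 11.2 records the change of estimand. Neither mentions the laboratory shift.

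**The case against.** The strongest reply has three parts.

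- **The protocol is not uniform.** Section 6.3.2 speaks of laboratory shift tables with no mention of grade or worst value, and Section 6.1 calls the protocol methods a summary of a fuller SAP. This stands as far as it goes: the SAP follows one protocol passage and omits another. It does not withdraw the specific commitment in 6.2.2, and added detail does not explain dropping a named output.
- **Important abnormalities appear elsewhere.** Adverse events are graded and tabulated by maximum severity and by discontinuation (SAP 9.1). Listings 16.2.8.1 to 16.2.8.3 show abnormal laboratory data. The by-visit summaries include a minimum and maximum (SAP 4.1). So individual values are not hidden. But Protocol 5.7.1 generally keeps findings without clinical significance out of the adverse events and, where applicable, records the sequelae rather than the laboratory finding. A listing, or one extreme value per visit, does not count subjects by severity and arm.
- **Only descriptive output is involved.** SAP Section 9 plans no inferential safety tests. This is correct and limits the weight of the point.

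A reader might also infer more than the documents support:

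- *That most extra results are lost.* To Day 57, the Week 4 and Week 8 windows cover 20 + 15 = 35 of 56 post-baseline days, or 62.5%. That is a share of days, not of samples; the documents give no frequency of extra draws.
- *That a transient peak appears in no table.* A Day 2 to 22 result, or one replacing a missed draw, may enter.
- *That the missing table would show how often the laboratory stopping rule in Protocol 5.9 was met.* That rule combines Grade 3, confirmation by repeat sample, and the judgement of the investigator or medical monitor. A worst-grade table shows only the first.

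**Conclusion.** The point holds. A specific, graded, worst-value laboratory table promised in the protocol is absent from the SAP text and from its table list, and the absence is not recorded as a change. The planned tables cannot show by arm how severe the worst value was, and they hide worsening in subjects already out of range at baseline.

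Its size is moderate: three shift tables lack the promised content, while alpha, power and efficacy conclusions are untouched. The conclusion rests on reading SAP 6.1.5.1 as covering laboratory tests, which follows from its scope of non-diary assessments. How many subjects or results are affected cannot be estimated from the documents.

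**What to change.** Add to SAP 9.3 and to the SAP 14.1 table list a shift from baseline grade to worst post-baseline grade, by analyte and arm, drawn from all post-baseline results including unscheduled and repeat samples. State explicitly that this table is exempt from the rule in SAP 6.1.5.1. To make it programmable:

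- name the laboratory grading scale;
- treat high and low directions separately for two-sided analytes such as sodium, potassium and glucose (all in Protocol Table 2);
- for analytes that the scale does not grade, use normal-range categories for the worst low and the worst high value.

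SAP V3.0 already postdates unblinding, so note the addition and its date in Section 11 and in the study report. If the sponsor decides not to produce the table, the departure from Protocol 6.2.2 should be recorded and justified in the same places; that corrects the record but leaves the gap.

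The cost is a few more descriptive tables and the derivation of grades from data already collected. No new sampling is needed.
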